6.2 Point of Enrollment

Subjects who have signed and dated the Informed Consent Form are considered enrolled in the study.

Adverse events will be captured beginning on the Consent Date. Adverse events occurring prior to the Index Procedure / Rescheduled Index Procedure will be analyzed and listed separately and will not otherwise be part of the outcome analyses specified in this protocol.

Screening tests that are part of standard-of-care (SOC) can be used to determine pre-eligibility, but no study-related activities, testing, procedures, etc. can take place until the ICF is signed and dated by the subject. Study data from exams performed prior to consent / enrollment (e.g., transthoracic echocardiography [TTE]) will be collected as medical history data after the subject is consented / enrolled in the study.

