6.6.3 Intent Subjects

Intent Subjects include the following types of subjects:

- Any subject who signs informed consent, meets eligibility criteria, but does not have any study investigational devices inserted into the body.
- Any subject that is enrolled in the study but does not undergo the Index Procedure within 30 days from the Consent Date or a Rescheduled Index Procedure within 45 days of the Index Procedure. These subjects will be withdrawn from the study as of the end of the above disqualifying interval.

Intent Subjects:

- Do not count towards the Treatment Subject enrollment ceiling
- Have no follow-up requirements once classified as an Intent Subject
- Will not be used for analysis of any study endpoints
- Will not be allowed to re-enroll in the study

For Intent Subjects, at a minimum the following forms must be completed:

- Enrollment and baseline CRFs such as, but not limited to, informed consent, enrollment information and other related CRFs
- End of Study CRF
- Adverse Event CRFs for any reportable event as defined in **Section 17.1** for any adverse event that occurs after signing the Informed Consent, up to the point of subject withdrawal

The original signed Informed Consent must be maintained in the investigation site's patient file. A subject ID will be assigned in the EDC system.

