6.6.4 Attempt Subjects

An Attempt Subject is a subject who signs informed consent, meets eligibility criteria, and has any investigational device inserted into the body but does not receive any pulsed field ablation application.

Attempt Subjects:

- Do not count towards the Treatment Subject enrollment ceiling.
- Will be followed up to the Day 30 assessment with all applicable CRFs completed
- Will be used for analysis of the study safety outcomes
- Will not be used for analysis of the study effectiveness outcomes including subgroup, multivariable, and center pooling analyses.
- Will not be allowed to re-enroll in the study.

For Attempt Subjects, at a minimum the following forms must be completed:

- Enrollment and baseline CRFs such as, but not limited to, informed consent, enrollment information and other related CRFs
- End of Study CRF
- Adverse Event CRFs for any reportable event as defined in **Section 17.1** for any adverse event that occurs after signing the Informed Consent, up to the point of subject withdrawal

The original signed Informed Consent for each Attempt Subject must be maintained in the investigation site's patient file. A subject ID will be assigned in the EDC system.

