7.6.2.1 Preparation

Subjects must be screened for substantial compliance with 4 weeks of systemic anticoagulation prior to the Index Procedure and, if in the opinion of the Investigator, this condition has not been met, the subject will be rescheduled as defined in Section 7.6.3.

TEE or volumetric CT within 48 hours of the procedure or ICE during the procedure will be utilized prior to transseptal puncture for exclusion of LA thrombus. If the study reveals atrial thrombus, the investigational procedure will not begin or will be terminated, no ablation will be performed, and the subject will be rescheduled as defined in Section 7.6.3.

Phrenic nerve function will be assessed prior to ablation per Investigator standard of care, preferably by a pre-sedation fluoroscopic sniff test. Subjects will undergo sedation / anesthesia according to institutional protocol. They will then be prepared in conventional sterile fashion for a cardiac catheterization procedure.

Femoral vein access will be obtained aseptically under ultrasound guidance.

Commercially available diagnostic catheters may be placed before or after transseptal access at the Investigator's discretion. Transseptal access to the LA will be obtained using commercially available devices, establishing guidewire access to the LA.

A heparin bolus will be delivered prior to or immediately after transseptal puncture. Procedural ACTs will be monitored according to the investigational site's standard of care and maintained at a minimum of 300 seconds at least until all devices are withdrawn from the left atrium.

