7.6.3 Rescheduled Index Procedure

If, at the Index Procedure, the subject is found to have inadequate pre-procedural anticoagulation, a current atrial thrombus, COVID-19, or other temporarily disqualifying condition, the subject may have their Index Procedure rescheduled not later than 45 days later. The Rescheduled Index Procedure will otherwise follow the data and procedural requirements of **Section 7.6.1**.

The Rescheduled Index Procedure must be scheduled within 45 days of the Index Procedure, and only one Rescheduled Index Procedure may be allowed; otherwise, the subject will be exited from the study as an Intent Subject.

This rescheduling is permissible and does not create an Acute Procedural Failure. The subject remains a potential Treatment Subject.

⁸ If anesthesia necessitates, a pre-discharge fluoroscopic sniff test or inspiration / expiration CXR may be acceptable. See **Section 7.7**.

References to “Index Procedure” in this protocol should be assumed when appropriate to include “Rescheduled Index Procedure” as well if not otherwise specified.

7.7 *Pre-Discharge Assessment*

Subjects should be prescribed a form of systemic anticoagulation treatment for at least two months following the ablation procedure. See **Section 7.3** regarding post-ablation anticoagulation requirements.

Type of Assessment: In-person at investigational site

Prior to hospital discharge, study data will be collected including but not limited to:

[figure not shown]
- Adverse events
- Hematocrit, hemoglobin, electrolytes, BUN, creatinine
- 12-lead ECG to document the subject’s rhythm and if any new conduction disturbances are observed.
 - A 12-lead ECG collected at the end of the Index Procedure / Rescheduled Index Procedure after all ablation was complete is also acceptable.
- Data regarding the use, changes in or discontinuation of anticoagulation, rate control and / or AADs.
- Occurrence, date, indication and outcome of any post-procedure cardioversion(s)
- Phrenic nerve assessment, as only applicable:
 - If the function of both phrenic nerves could not be confirmed at the end of the Index Procedure / Rescheduled Index Procedure, a radiologic examination of the diaphragm (fluoroscopic sniff test or inspiration / expiration CXR)
 - If the post-Index Procedure / Rescheduled Index Procedure fluoroscopy indicated diminished phrenic nerve response and resolution has not been previously demonstrated, a radiologic examination of the diaphragm

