8.1.1.1 Hypotheses

Let P be the proportion of Treatment Subjects and Attempt Subjects with one or more CSAEs through the Day 360 Assessment (Treatment) or Day 30 Assessment (Attempt) and PG be the performance goal, the following hypothesis will be tested in a one-sided test at 0.025 significance level.

- $H_0: P \geq PG$
- $H_A: P < PG$

Where PG = 12%.

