23.2 Definitions

Protocol terms not otherwise defined in the protocol are defined in **Table 23.2-1**:

Table 23.2-1: Definitions

Term	Definition
Acute Procedural Success	
 Persistent AF Acute Procedural Success is defined in Section 3.3.1. CTI-Mediated Flutter Acute Procedural Success is defined in Section 3.4.2
Antiarrhythmic Drugs, Class I and III	
Class I / III AADs are those pharmaceutical agents approved or used in the relevant jurisdiction for the treatment of cardiac arrhythmia. For the ADVANTAGE AF Study, Class I and III AADs include but are not limited to:
 
 Class I, sodium channel blockers: disopyramide, flecainide, procainamide, propafenone, quinidine. Class III, potassium channel blockers: amiodarone, dofetilide, dronedarone, sotalol. 
Should other Class I or III AADs become approved or used in the relevant jurisdiction for the treatment of cardiac arrhythmia during the ADVANTAGE AF Study, they will be considered as Class I / III AADs for this protocol.

Attempt Subjects	Attempt Subjects are defined in Section 6.6.4 .
Blanking Period	
An interval in which recurrent AF, AFL or AT, cardioversion or a first re-ablation do not constitute Treatment Failure beginning on Day 0 and running for 90 days thereafter.
 
 The Blanking Period has no impact on the assessment of AEs. For subjects with only an Index Procedure, the Blanking Period will be Day 0 to Day 90 inclusive. For subjects who require a Rescheduled Index Procedure, the Blanking Period will be the Study Day of the Rescheduled Index Procedure (Day 0) plus 90 days inclusive For subjects treated with a Non-Failed AAD during the Blanking Period, a Treatment Failure due to the use of that drug only occurs if there is continued use of that drug following the earlier of either the Day 90 visit or Day 104.
Chronic Success	
 Persistent AF Chronic Success is defined in Section 3.3.2. CTI-Mediated Flutter Chronic Success is defined in Section 3.4.2
Composite Serious Adverse Events	Composite Serious Adverse Events are defined in Section 3.2 .

Term	Definition

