7.7.3 Rescheduled Index Procedure

If, at the Index Procedure, the subject is found to have inadequate pre-procedural anticoagulation, a current atrial thrombus, COVID-19, or other temporarily disqualifying condition, the subject may have their Index Procedure rescheduled not later than 45 days later. The Rescheduled Index Procedure will otherwise follow the data and procedural requirements of **Section 7.7.2**.

The Rescheduled Index Procedure must be scheduled within 45 days of the Index Procedure, and only one Rescheduled Index Procedure may be allowed; otherwise, the subject will be exited from the study as an Intent Subject.

This rescheduling is permissible and does not create an Acute Procedural Failure. The subject remains a potential Treatment Subject.

References to “Index Procedure” in this protocol should be assumed when appropriate to include “Rescheduled Index Procedure” as well if not otherwise specified.

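### The Intent and Attempt definitions conflict for a subject whose Index Procedure is stopped after device insertion, so a device-related event there can fall outside the primary safety endpoint.

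*Combined protocol and SAP*

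**What the plan says.** **Classification.** Section 6.6.4 defines an Attempt Subject as an eligible, consented subject who "has any investigational device inserted into the body but does not receive any pulsed field ablation application". Attempt Subjects are followed to Day 30 and belong to the primary safety endpoint (PSE) set. Section 6.6.3 gives two alternative definitions of Intent. The first bullet requires that no investigational device was inserted. The second depends only on time: no Index Procedure within 30 days of consent, or no Rescheduled Index Procedure within 45 days of the Index Procedure. Intent Subjects have no follow-up requirement and "Will not be used for analysis of any study endpoints". Section 6.1.3 says that a subject who misses these time limits is Intent or Consent Ineligible, depending on circumstances. Section 7.6.3 adds that "only one Rescheduled Index Procedure may be allowed; otherwise, the subject will be exited from the study as an Intent Subject", and Appendix A 7.7.3 repeats that "otherwise, the subject will be exited from the study as an Intent Subject". None of these timing rules makes an exception for a device already inserted.

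**Stopped procedures.** If thrombus is found, Section 7.6.2.1 says "the investigational procedure will not begin or will be terminated, no ablation will be performed, and the subject will be rescheduled". Section 7.6.3 also allows rescheduling for other temporary disqualifying conditions, which it does not list.

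**Time zero.** For a rescheduled subject, Section 23.2 says "the Blanking Period will be the Study Day of the Rescheduled Index Procedure (Day 0) plus 90 days inclusive". The same table defines the Start Date as the date of the Index or the Rescheduled Index Procedure, without saying which applies when both took place. Under Section 6.2, adverse events before the Index / Rescheduled Index Procedure "will be analyzed and listed separately and will not otherwise be part of the outcome analyses specified in this protocol". The onset windows in Section 3.2 are counted from Day 0 (to Day 7, Day 30 or the Day 360 Assessment). In Appendix A 3.3 the longest window ends at Day 90.

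**The concern.** The PSE is meant to cover every subject in whom the investigational system was used, including those who received no application. Two sets of rules can take a subject out.

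1. **Not re-treated in time.** The subject meets Section 6.6.4 and also the second bullet of Section 6.6.3. If the site or the data system applies the timing rule, the subject leaves without Day 30 follow-up and enters no endpoint.
2. **Re-treated.** The subject becomes a Treatment Subject with Day 0 at the later procedure. A composite serious adverse event (CSAE) from the stopped procedure may then count as preceding Day 0.

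Either omission lowers the reported CSAE rate, and the test compares an upper limit with a goal. It may also depend on outcome, since a subject harmed at a stopped procedure is less likely to return within 45 days. The censoring rules in Section 8.1.1.3 and the Phase 2 tipping-point analysis (Appendix A 8.3.3.1) cannot repair this. They act on subjects in the analysis set with time counted from Day 0, and these subjects are outside the set or their event predates it.

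**Working it through.** **The plan's own figures.** Inputs from Sections 8.1.1.1 and 8.1.1.2: goal 12%, expected rate 6%, "tested in a one-sided test at 0.025 significance level", 232 evaluable, 86% power, 10% attrition.

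- Exact binomial at N = 232: the largest c with P(X ≤ c | 12%) ≤ 0.025 is c = 18. Alpha is 0.0246 and power P(X ≤ 18 | 6%) is 89.4%.
- The stated 86% reproduces as a floor: 232 is the smallest N from which exact power stays at or above 86% for every larger N (minimum 86.2%, at N = 241).
- 232 / 0.90 = 257.8, giving 258. Phase 2: 245 / 0.95 = 257.9, giving 258.

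The design figures stand, and this point changes none of them.

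**The rules side by side** (device inserted, no application delivered, procedure stopped).

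| What happens next | Rule | Status | In the PSE? |
|---|---|---|---|
| Not re-treated within 45 days | 6.6.4 | Attempt | Yes |
| Not re-treated within 45 days | 6.6.3 second bullet, 6.1.3, 7.6.3 | Intent or Consent Ineligible | No |
| Re-treated | 6.2 and 23.2, with Day 0 at the later date | Treatment | Earlier event can be read as excluded |
| Re-treated | 3.2, if it covers both procedures | Treatment | Earlier event can be read as counted |

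**Pass boundary.** Section 8.1.1.3 uses a Kaplan-Meier estimate with a log-log limit. With no censoring and x events in n subjects, S = 1 − x/n, se(log S) = √[x / (n(n − x))], v = se / |log S|, and the upper limit is 1 − exp{−|log S| · exp(1.96 v)}.

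- x = 20, n = 258: S = 0.9225, |log S| = 0.0807, se = 0.01805, v = 0.2237; upper limit 11.76%, pass.
- x = 21, n = 258: S = 0.9186, |log S| = 0.0849, se = 0.01853, v = 0.2183; upper limit 12.21%, fail.
- n = 245 (Phase 2 evaluable): 19 events give 11.89%, pass; 20 give 12.37%, fail.

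**Sensitivity to k omitted events.** The documents give no k; 0 to 3 is an assumed range. For n = 258 the chance of passing at a true rate of 12% is P(X ≤ 20 + k | 258, 12%). For n = 245 it is P(X ≤ 19 + k | 245, 12%).

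| k | Upper limit with all 20 + k events counted (n = 258) | Chance of passing, n = 258 | Chance of passing, n = 245 |
|---|---|---|---|
| 0 | 11.76% | 1.8% | 2.1% |
| 1 | 12.21% | 3.0% | 3.5% |
| 2 | 12.66% | 4.8% | 5.5% |
| 3 | 13.11% | 7.2% | 8.4% |

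For n = 258 the reported limit stays between 11.76% and 11.89%, whether the omitted subjects remain in the denominator or leave it. If instead a share of CSAEs is assumed lost (5%, 10%, 15%), the chance of passing at a true 12% goes from 1.8% to 3.5%, 6.5% and 11.3%. At the planned 6% rate it is already 90.2% with nothing lost.

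**The case against.** **Override.** A reader might infer that the rescheduling rules override Attempt status. The documents do not say so. No precedence is stated, the first Intent bullet requires that no device was inserted, and Appendix A Section 6 treats insertion as the dividing line for a subject who withdraws after receiving only the cardiac monitor. This stands: the defect is an unresolved conflict.

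**Eligibility.** A reader might also infer that a new thrombus makes the subject ineligible and so not an Attempt Subject. Section 5.3 names left atrial thrombus as remediable, and the footnote to Section 6.6.1 says such criteria are not an ultimate eligibility failure. The inference would hold only if the condition never resolved.

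**A narrow route.** Anticoagulation is screened beforehand, thrombus is looked for before transseptal puncture, and transseptal access uses commercial devices. Appendix A 7.7.2.1 stops the procedure for thrombus before left atrial access. Treating a complication of the procedure as a temporary disqualifying condition goes beyond the text, whose examples are conditions the subject is found to have. This largely stands. The route stays open because Phase 1 says only that the procedure is terminated, the list of conditions is open-ended, and the sheath is itself an investigational device.

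**Events before re-treatment.** Section 3.2 names the Index Procedure among those that count and ties onset to the procedure. Appendix A 17.1 starts the Index Procedure at device insertion, so a later event would not precede it. The Blanking Period definition has no bearing on adverse events, and the events committee adjudicates all serious events. Hence a reader should not conclude that such events are definitely excluded. But Section 3.2 does not say that both procedures count, and adjudicating an event does not settle its window.

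**Materiality.** Any threshold test can turn on one event, and several CSAE components presuppose ablation. That is fair, and the loss figures above remain assumptions.

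**Conclusion.** The concern holds as a conflict in the text. A subject with a device inserted at a stopped Index Procedure and not re-treated within 45 days is both Intent and Attempt. For one who is re-treated, the plan does not say whether a CSAE from the stopped procedure counts. Followed literally, the timing rules can drop device-related events from the primary safety test in both phases.

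The direction favours the device. The size is unknown, and probably few subjects are affected. The one-event reversal at the boundary assumes 258 subjects and no censoring. The false-pass probabilities of 3.0% to 7.2% further assume one to three omitted events and a true rate of exactly 12%; they are not estimates of the trial's error rate. This merits correction before analysis, but it does not show that the test is invalid or that any event has been lost.

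**What to change.** Reconcile the passages, with device insertion as the dividing line throughout.

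- **Sections 6.1.3, 6.6.3, 7.6.3 and Appendix A 7.7.3:** limit Intent / Consent Ineligible status to subjects with no investigational device inserted at any procedure. A subject with a device inserted stays in the PSE set as Attempt, or as Treatment once an application is delivered.
- **Sections 3.2 and 6.2 and Appendix A 3.3:** state that, for the PSE, a CSAE with onset after device insertion at a stopped Index Procedure counts, with the onset windows run from that procedure as well as from the Rescheduled Index Procedure.
- **Unchanged:** Day 0 for effectiveness, the Blanking Period, sample size, alpha and power.

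The cost is protocol and SAP wording and the existing Day 30 contact for a few subjects who are not re-treated. The observed CSAE rate may be slightly less favourable.

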7.8 Day 7 Safety Assessment

Type of Assessment: Remote
Window: Days 7 – 11
The Day 7 Assessment is essential to establish the primary safety endpoint and every effort must be made to complete this assessment between Day 7 and Day 11.
If the assessment is delayed, the onset date of an AE must be elicited as carefully as possible to establish whether it occurred within the interval between the ablation procedure and Day 7, or thereafter.

Subjects will be assessed remotely between Day 7 and 11 post-Index Procedure / Rescheduled Index Procedure. Any subject who continues to be hospitalized at the time of the assessment will have their Day 7 assessment performed in-hospital.

Study data will be collected by interview, including but not limited to:

- Adverse events
- Data regarding the use, changes in or discontinuation of anticoagulation, rate control and / or AADs.
- Recurrent arrhythmia, cardioversions, ablations, or hospital admissions since discharge
- The date and communication method(s) used to collect the data remotely

7.9 Day 30 Safety Assessment

Type of Assessment: Remote
Window: Days 30 – Day 37
The Day 30 Assessment is essential to establish the primary safety endpoint and every effort must be made to complete this assessment between Day 30 and Day 37.
If the assessment is delayed, the onset date of an AE must be elicited as carefully as possible to establish whether it occurred within the interval between the ablation procedure and Day 30, or thereafter.

AAD Treatment: Between the Day 30 Assessment and the Day 90 Assessment – the subject should be assessed for AAD continuation. See Section 7.10.

Discharged subjects will be assessed remotely between Day 30 and Day 37 post-Index Procedure / Rescheduled Index Procedure. Any subject who is hospitalized at the time of the assessment will have their Day 30 assessment performed in-hospital.

Study data will be collected by interview including but not limited to:

- Adverse events
- Data regarding the use, changes in or discontinuation of anticoagulation, rate control and / or AADs.
- Recurrent arrhythmia, cardioversions, ablations, or hospital admissions since 7-day telephonic assessment
- The date and communication method(s) used to collect the data remotely

7.10 Day 90 Assessment

Type of Assessment: In-person at investigational site required; remote only for documented COVID-19 related disruption.

Window: 90 ± 14 Days

If a COVID-19-related disruption prevents an in-person assessment within window:

- As much data as possible may be collected remotely.
- The absence of a 12-lead ECG during a remote assessment is not a protocol deviation but the subject should make an EM transmission at the time of the assessment.
- If a radiologic examination is required due to prior diminished phrenic nerve response, an inspiration / expiration chest X-ray (CXR) performed in-person or at another healthcare site may be substituted.

Event Monitoring: Prior to or at the scheduled Day 90 Assessment, the subject will receive event monitor (EM) hardware and training regarding its use and the importance of event monitoring. The subject will be instructed to begin using the twice per month EM recordings starting at the time of the Day 90 Assessment and also for any symptomatic episodes experienced at any time throughout the remainder of study follow-up.

The subject will be reminded of the critical importance of full compliance with rhythm monitoring both for successful treatment of their arrhythmia and for the success of the study.

AAD Treatment: During the Blanking Period the subject should be assessed for AAD continuation.

At Investigator discretion, Class I / III AADs may be stopped to allow assessment of the subject's potential for off-drug freedom from recurrent AF, AFL, or AT.

Subjects who require continued AAD treatment may be continued; preferably with a Failed AAD. Using a Non-Failed AAD or amiodarone would create an unnecessary Treatment Failure. See Section 7.4.

Subjects will be assessed at Day 90 ± 14 days following the Index Procedure / Rescheduled Index Procedure. Study data will be collected at the Day 90 Assessment including but not limited to:

- Adverse events

- Data regarding the use, changes in or discontinuation of anticoagulation, rate control and / or AADs
- Recurrent arrhythmia, cardioversions, ablations, or hospital admissions since last assessment
- Cardiac rhythm as determined by a 12-lead ECG at the time of the assessment (in-person assessment only). All 12-lead ECGs will be provided to the Arrhythmia Core Laboratory (ACL).
- If the post-Index Procedure / Rescheduled Index Procedure fluoroscopy indicated diminished phrenic nerve response and resolution has not been previously demonstrated, a radiologic examination of the diaphragm
- If there is a clinical suspicion of PV stenosis, a cardiac CT or MRI scan of the same type as the baseline scan to assess the dimensions of the PVs.
- If data is collected remotely, the date, time and communication method(s) used to collect the data remotely.

